4.3.3 Sensitivity Analysis

In order to assess the robustness of the primary analysis model with respect to non-monotone missing data, the primary efficacy endpoint will be analyzed using a mixed model repeated measures (MMRM) with baseline, treatment (low dose or high dose), time (all available visit weeks through Week 48), and treatment by time interaction as fixed effects and participant as

random effect. The change from baseline in hours of ventilation support at Week 24 will be summarized by dose level based on this model, including the 95% confidence interval.

The same analysis set and data used for the primary analysis (including imputations) will be used for the sensitivity analysis.

4.4 Secondary Endpoints Analysis

4.4.1 Key Secondary Endpoint

4.4.1.1 Definition of Endpoint

Percentage of participants achieving functionally independent sitting for at least 30 seconds by Week 24.

The primary source of data is the motor milestone eCRF. However, if that data isn't available for the visit, then Bayley III item #26 will be used to determine whether the participant achieves (Yes) or doesn't achieve (No) the milestone.

If both the motor milestone or the Bayley result are not available, but the participant attended the visit, then their result will be included in the summary as "missing".

4.4.1.2 Main Analytical Approach

The analysis of the key secondary endpoint will be conducted using the FAS.

The number and percentage of participants achieving functionally independent sitting for at least 30 seconds by Week 24 will be summarized descriptively by low dose and high dose groups.

In addition, the number and percentage of participants achieving functionally independent sitting for at least 30 seconds will be summarized descriptively by visit and dose level group.

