Following the occurrence of fatal serious AEs (SAEs) in Study ATX-MTM-002, the Sponsor, in consultation with the DMC and external experts, evaluated the data and reassessed the benefit/risk profiles of the 1.0×10^{14} vg/kg and 3.0×10^{14} vg/kg dose levels. As of the data cutoff date of 08 July 2020, 5 subjects who received 3.0×10^{14} vg/kg AT132 developed AT132-related SAEs involving the hepatobiliary system. In 2 subjects, these SAEs resolved; in 3 subjects, fatal events occurred subsequent to severe cholestatic liver dysfunction. Within the 3.0×10^{14} vg/kg dose level cohort, 8 of 17 subjects (47.1%) experienced 26 SAEs considered related to AT132. In contrast, within the 6 subjects dosed at the 1.0×10^{14} vg/kg dose level, all of whom are ≥ 2 years from AT132 administration, 1 (16.7%) subject experienced 4 AT132-related SAEs, all resolved, and none involved the hepatobiliary system. In addition to a favorable safety profile observed in the subjects treated with 1.0×10^{14} vg/kg, a clinically meaningful benefit continues to be observed in this group at last follow-up. In this group, which had a mean 20.5 hours (SE 2.02) of ventilation per day at baseline ($n = 5$ [83.3%] with invasive ventilation; $n = 1$ [16.7%] with non-invasive ventilation), 5 out of 6 (83.3%) subjects were ventilatory independent at last follow-up (as of data cutoff date 08 July 2020). With respect to gross motor development, at baseline 5 of the 6 subjects did not perform any of the following major motor milestones: sit unassisted for 30 seconds, raise self to standing position, stand alone, or walk alone. At baseline, 1 subject did sit unassisted for 30 seconds but did not perform the remaining motor tasks. At last follow-up following AT132 administration at 1.0×10^{14} vg/kg, 5 out of 6 subjects performed all of these motor tasks, including walking alone. Regarding performance on the Children's Hospital of Philadelphia Infant Test of Neuromuscular Disorders (CHOP INTEND), this 1.0×10^{14} vg/kg group demonstrated a baseline mean score of 37.7 (SE 2.42). At last follow-up, performance had improved to a mean score of 56.5 (3.97).

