14. Subject is able to sit without assistance for at least 30 seconds at screening, in the opinion of the Investigator (Part 2 including any subjects enrolled under protocol v8 and beyond).
15. Subject has a clinically important condition, including CTCAE v4.03 Grade ≥ 2 anemia (< 10 g/dL hemoglobin).*
16. Subject has a contraindication to ursodiol (ursodeoxycholic acid).*
17. UNIQUE to France: Subject has a prior diagnosis or history of cardiac arrhythmias, myocarditis, or any other cardiac disease.
18. UNIQUE to France: Subject has a contraindication to general anesthesia and to muscle biopsy procedures.

* If a subject is a delayed-treatment control, this inclusion/exclusion criterion must be met before receiving AT132.

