‡ Duration of sitting in the reference (WHO Multicenter Growth Reference Study) is not clearly defined, so the same age is used for the expected age of achievement for both independent sitting milestones.

The number and percentage of participants achieving each gross motor function milestone will be summarized descriptively by low dose and high dose group by visit week through Week 24. A similar summary will be provided for visits occurring after Week 24.

The denominator of the percentage calculation will only include the participants who attended the visit and are expected to achieve the particular milestone based on their age (i.e., if at the time of an assessment the child is at least the age indicated in [Table 1](#), then they will be considered eligible for the milestone and will be included in the denominator). A child’s eligibility will need to be uniquely determined for each assessment at each time-point.

The denominator values will be included in the table.

The percent of age-eligible milestones that each participant achieves at Week 24 will also be summarized as a continuous (percentage) by visit and via shift table as an ordinal variable, by number and percent of participants in each category (None, at least 1, >1 to half of the expected milestones, >50% to <100% all expected milestones, All expected milestones) at baseline and shift post-baseline.

Number of age-eligible milestones expected at Week 24 (denominator for the calculation for the participant at the visit) is determined based on the age of the participant at the visit and the corresponding number of milestones expected for that age. The numerator of the calculation for the participant at the visit is the number of milestones that they have achieved. The corresponding percentage will be converted to the relevant category. The number of participants falling into each category regardless of age will be summarized at each visit.

Each participant's timeline of achieving the motor milestones will also be presented graphically.

Any assessment done prior to the date of the participant signing Protocol V 5.0 informed consent is assumed to correspond to protocol V1.0 – 4.0 data.

4.4.2.2.7 Percentage of participants achieving full ventilator independence at Week 24

“Full ventilator independence” is defined as: the date of removal from ventilator field on the “Assessment of Ventilator Parameters” eCRF is not blank or “Is subject on a ventilator” = “No” on the same eCRF.

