4.5.1.2 Main Analytical Approach

4.5.1.2.1 Time to unassisted sitting for 30 seconds or more at Week 24

This endpoint will be summarized for low dose and the high dose groups separately for all participants in the FAS. Kaplan-Meier plots along with median (95% CI) time from the study start date to event will be provided.

The event of successful unassisted sitting for 30 seconds is defined as described in [Section 4.4.1.1](#). Participants who meet the described criteria will be considered to have an event. All other participants will be censored

4.5.1.2.2 Change from baseline in the Motor Function Measure-32 (MFM-32) at Week 24

MFM-20 and MFM-32 total and dimension scores will be summarized descriptively by visit and dose level group. For the MFM-20 by-visit summary, if participants were administered the MFM-32, then the MFM-20 questions/derivations will be used from those assessments to derive the MFM-20 result for summary purposes.

Regardless of whether the participants were administered MFM-32 or MFM-20, the observed total and dimension scores and corresponding change from baseline at each visit will be listed. The listing will include a column indicating which version of the questionnaire was administered at the visit.

4.5.1.2.2.1 MFM-32 Scoring

The MFM-32 contains 32 items to assess motor function, each measured on a scale of 0 to 3, for a total score of 96. The measures capture 3 dimensions of motor function:

- Standing and transfers (D1: 13 Items 6, 8, 11, 12, 24, 25, 26, 27, 28, 29, 30, 31 and 32)
- Axial and proximal motor function (D2: 12 Items 1, 2, 3, 5, 7, 9, 10, 13, 14, 15, 16 and 23)
- Distal motor function (D3: 7 Items 4, 17, 18, 19, 20, 21, and 22)

The score for each dimension corresponds to the sum of the scores obtained by the person for the items of this dimension divided by the maximum score for this dimension and multiplied by 100. For the unilateral items, the best score of the two sides at each visit will be used.

For the MFM-32, the total score is the sum of the 32 items scores divided by 96, as shown in the table below:

Table 2 MFM-32 Scoring

Measurement	Calculation
D1: Standing and Transfers	$D1\% = \frac{\text{Sum of D1 score}}{13 \times 3 = 39} * 100$
D2: Axial and Proximal	$D2\% = \frac{\text{Sum of D2 score}}{12 \times 3 = 36} * 100$
D3: Distal Motor Function	$D3\% = \frac{\text{Sum of D3 score}}{7 \times 3 = 21} * 100$
Total	$\text{Total}\% = \frac{\text{Sum of total score}}{32 \times 3 = 96} * 100$

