4.5.1.2.5 Change from baseline in the proportion of participants being able to feed without a gastrostomy or G-tube at Week 24

A participant’s ability to feed without a gastrostomy tube (G-tube) is evaluated by the Parental Swallowing Questionnaire. A participant score of “Never (0)” on the first item of the

questionnaire, “Since the last visit how often do you use the following with your child – Tube Feeding” will indicate that the participant met the criteria in the endpoint at the visit.

A shift table of the number and proportion of participants meeting the criteria described above will be presented by dose level. The shift from baseline G-tube status to best post-baseline G-tube status will be summarized, as well as the shifts to each visit.

4.5.1.2.6 Change from baseline in the Communicative Development Inventories scores at Week 24

The Communicative Development Inventories scores and corresponding change from baseline at each visit will be summarized descriptively by dose level group.

CDI scores for each participant will be calculated as number of items marked by caregiver/ number of items on questionnaire. This is a raw, unadjusted score.

4.5.1.2.7 Change from baseline in the Parental Global Impression of Secretion Severity (PGIS-S) score at Week 24

The PGIS-S scores and corresponding change from baseline at each visit will be summarized descriptively by dose level group.

Parents/LAR/caregiver will report on the amount of suctioning and secretions management required over the previous week, using a scale of 1 to 7 (1 = not affected and 7 = among the worst he has ever been) to report impression of change from baseline and impression of current severity.

Missing values will not be imputed.

4.5.1.2.8 Change in the Parental Global Impression of Secretion Improvement (PGIS-I) score at Week 24

The PGIS-I scores at each visit will be summarized descriptively by dose level group.

Parents/LAR/caregiver will report on the amount of suctioning and secretions management required over the previous week, using a scale of 1 to 7 (1=very much improved and 7 = very much worse) to report impression of change from baseline.

Missing values will not be imputed.

4.5.1.2.9 Change from baseline in Clinical Global Impression of Severity (CGI-S) at Week 24

The CGI-S scores and corresponding change from baseline at each visit will be summarized descriptively by dose level group.

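### The key secondary sitting rate and the time-to-sitting curve do not require sitting to be newly gained, so a known low-dose baseline sitter can count as a success

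*SAP*

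**What the plan says.** The endpoint in SAP 4.4.1.1 is: "Percentage of participants achieving functionally independent sitting for at least 30 seconds by Week 24". Each visit is scored Yes or No from the motor milestone eCRF or, failing that, from Bayley-III item 26. SAP 4.4.1.2 then says: "The number and percentage of participants achieving functionally independent sitting for at least 30 seconds by Week 24 will be summarized descriptively", by dose group and in the FAS. SAP 3 admits to the FAS anyone dosed who has at least one post-dose efficacy assessment; baseline motor ability plays no part.

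Time to unassisted sitting (SAP 4.5.1.2.1) covers every FAS participant and points back to 4.4.1.1 for the event: "Participants who meet the described criteria will be considered to have an event".

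Eligibility closes the gap only in part. Exclusion Criterion 14 (Protocol 3.3.2) reads: "Subject is able to sit without assistance for at least 30 seconds at screening, in the opinion of the Investigator (Part 2 including any subjects". The criterion goes on to include subjects enrolled under v8 and later, so Part 1 children were not covered. Of the six children treated at the low dose by the July 2020 cutoff, Protocol 1.4.2 says: "At baseline, 1 subject did sit unassisted for 30 seconds but did not perform the remaining motor tasks".

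Elsewhere the SAP does relate outcome to baseline. The percentage of age-eligible milestones is summarised "by visit and via shift table as an ordinal variable, by number and percent of participants in each category", running from baseline to post-baseline (4.4.2.2.6). For feeding (4.5.1.2.5): "The shift from baseline G-tube status to best post-baseline G-tube status will be summarized".

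**The concern.** A responder rate after a single gene-therapy dose will be read as the share of children who gained the ability. As written, it combines children who gained sitting with any who had it before dosing. In a low-dose group of about seven, one child is a large share of the percentage.

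The problem comes from joining two features of the plan. The criterion that fits a sitting endpoint was limited to Part 2 and v8 onward. The current SAP makes sitting the key secondary endpoint and analyses everyone by dose received, which brings Part 1 children in without a matching baseline rule. The low-dose group is mostly Part 1, and it contains the documented sitter.

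All output is descriptive (SAP 2), so no error rate or power is at stake. The reported rate and curve are themselves the result, and both would credit pre-treatment ability.

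**Working it through.** The documents give no assumed rate, sample size or Week 24 count for sitting, so there is no planning figure to reproduce. The N = 10 calculation in SAP 4.9 concerns ventilation hours and does not bear on this point. The size of the effect is therefore a range.

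**Inputs**
- Low-dose children at the July 2020 cutoff: 6, of whom 1 sat for 30 seconds at baseline and 5 did not (Protocol 1.4.2).
- Undosed delayed-treatment controls, to be given the low dose: 3 (Protocol 3.1, v8 and v9).
- Delayed controls never dosed: 2 (SAP 1.3).
- Replacement children could be enrolled for controls not eligible for dosing (Protocol 3.3.5).

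**Low-dose N.** 6 + 3 − 2 = 7. This is inferred and assumes no replacement was dosed. A later low-dose child fits the text: Protocol 1.5 reports a low-dose death involving hepatobiliary failure, whereas Protocol 1.4.2 says none of the related SAEs in the first six was hepatobiliary. One or two replacements would give N = 8 or 9. Added children are taken as baseline non-sitters, since Exclusion 14 applied to them at screening.

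**Formula.** Let k be the number of the N − 1 baseline non-sitters who gain sitting, and suppose the baseline sitter is scored Yes after dosing. With complete data the SAP reports (k + 1)/N. New attainment among non-sitters is k/(N − 1). The excess is

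(k + 1)/N − k/(N − 1) = (N − 1 − k) / [N(N − 1)].

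| N | k | SAP rate | New attainment | Excess (points) |
|---|---|---|---|---|
| 7 | 0 | 14.3% | 0.0% | 14.3 |
| 7 | 3 | 57.1% | 50.0% | 7.1 |
| 7 | 5 | 85.7% | 83.3% | 2.4 |
| 7 | 6 | 100% | 100% | 0 |
| 8 | 0 | 12.5% | 0.0% | 12.5 |
| 8 | 3 | 50.0% | 42.9% | 7.1 |
| 8 | 5 | 75.0% | 71.4% | 3.6 |
| 9 | 0 | 11.1% | 0.0% | 11.1 |
| 9 | 3 | 44.4% | 37.5% | 6.9 |
| 9 | 5 | 66.7% | 62.5% | 4.2 |

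The excess is never negative. It reaches zero only when every non-sitter gains sitting.

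**Kaplan-Meier.** With time counted from dosing and no earlier censoring, this child adds a step of 1/N at his first recorded post-dose assessment: 1/7 = 14.3 points, 1/8 = 12.5 or 1/9 = 11.1.

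**Do other outputs correct this?** Baseline ability to sit is tabulated (SAP 4.2.4), sitting is shown by visit (4.4.1.2), each milestone is summarised by visit (4.4.2.2.6), and each child's "timeline of achieving the motor milestones will also be presented graphically". A reader could trace the child from these, but none alters the headline rate or the curve. The milestone shift table works on the percentage of all age-eligible milestones and does not isolate sitting.

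**The case against.** **New attainment is not what the protocol asks for.** Protocol 2 words the endpoint as status at Week 24, where a baseline sitter properly counts, and Protocol 7.4.2.2.1 assigns it to the FAS. This stands as a reason to keep the all-FAS rate. It does not settle the reading, because the synopsis, Protocol 7.4.2.2.1 and the SAP all say by Week 24, and the word for achieving is turned into a plain visit-level Yes/No.

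**The comparators are selective.** The G-tube endpoint is by name a change from baseline, and the milestone shift table serves another variable. Full ventilator independence is a plain rate with no baseline condition. The first part is fair, but ventilator independence is not a closer match: Inclusion Criterion 4 requires ventilatory support at entry, so the baseline problem hardly arises there.

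**Little is hidden in a group of seven.** The baseline, by-visit and per-milestone tables and the timelines do allow tracing. That lowers the severity but does not correct the result.

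**The size is conditional.** SAP 4.4.2.2.6 says Bayley and milestone collection was intermittent under protocol versions 1 to 4, so this child's early results may be missing. The 14.3-point maximum needs no other low-dose child to gain sitting, and nothing in the documents supports that extreme. SAP 4.1 bases percentages on non-missing participants, so the denominators could be smaller. All of this stands as a limit on the range.

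**The curve's time origin is unclear.** SAP 4.5.1.2.1 counts from the study start date, which Protocol 3.7 defines as the first participant's consent. Taken literally, this moves where the step falls and, with earlier censoring, alters its height. It qualifies the exact 1/7 but does not remove the event.

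**Conclusion.** The concern holds. Followed as written, the SAP lets a child who sat for 30 seconds before dosing count as a low-dose key secondary success and as an event in the time-to-sitting curve.

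The low-dose rate would exceed new attainment by 0 to 14.3 points at N = 7. The maximum is 12.5 points at N = 8 and 11.1 at N = 9. This rests on the child being scored as sitting after dosing, complete data, the inferred N, and no second baseline sitter in the low-dose group. The last is likely but not certain, because Exclusion 14 is not among the criteria rechecked in delayed controls before dosing.

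The number of high-dose baseline sitters is not reported, and high-dose Part 1 children were also outside Exclusion 14, so the effect on the dose contrast is unknown. With no hypothesis testing this is not critical, but a named key secondary result should not credit pre-treatment ability when the correction is this cheap.

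**What to change.** In SAP 4.4.1.2, add the number and percentage newly attaining 30-second sitting by Week 24 among FAS participants who did not sit for 30 seconds at the pre-dose baseline (baseline as in SAP 4.10.1). In SAP 4.5.1.2.1, add time to sitting in the same children. List baseline sitters by dose group.

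Keep the all-FAS rate and curve beside these, since the protocol assigns the endpoint to the FAS, and leave the non-missing percentage rule of SAP 4.1 as it is. If the SAP is not reopened, the addition can be documented in the CSR, as SAP 1 provides.

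The cost is one baseline flag, one table row and one Kaplan-Meier summary, all from data already collected. The low-dose denominator for the new row falls from about 7 to 6, and at N = 7 its percentage will be 0 to 14.3 points less favourable than the all-FAS figure.

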ENDPOINTS, SAFETY ASSESSMENTS, AND ESTIMANDS: Primary Efficacy Endpoint: 
• Change from baseline in hours of ventilation support at Week 24 Key Secondary Efficacy Endpoint: 
• Percentage of subjects achieving functionally independent sitting for at least 30 seconds by Week 24 Other Secondary Efficacy Endpoints: 
• Time to reduction in required ventilator support to \leq 16 hours a day (only in subjects who require invasive ventilation) at Week 24

- Change from baseline in Children's Hospital of Philadelphia Infant Test of Neuromuscular Disorders (CHOP INTEND) at Week 24
- Change from baseline in maximal inspiratory pressure (MIP) at Week 24
- Change from baseline in quantitative analysis of myotubularin expression in the muscle biopsy at Week 24
- Change from baseline in quality of life assessments at Week 24 (ie, the Assessment of Caregiver Experience with Neuromuscular Disease [ACEND] and Pediatric Quality of Life Inventory [PedsQL])
- Number (%) of age-appropriate clinically relevant gross motor function milestones attained through Week 24
- Percentage of subjects achieving full ventilator independence at Week 24
- Survival

Safety Endpoints:

- Adverse events (AEs), serious AEs (SAEs), and findings from safety laboratory tests, 12-lead electrocardiogram (ECG), echocardiograms (ECHOs), vital signs, growth parameters, physical examinations, liver ultrasounds, antibody formation (anti-AAV8, anti-MTM1), viral shedding, annualized hospitalization rate, annualized respiratory and non-respiratory SAE rate, and length of stay per hospitalization

Exploratory Endpoints:

- Time to unassisted sitting for 30 seconds or more at Week 24
- Change from baseline in the Motor Function Measure scale (MFM-32) at Week 24
- Change from baseline in total raw score in the gross motor domain of the Bayley Scales of Infant and Toddler Development III (Bayley-III) at Week 24
- Change from baseline in total raw score in the fine motor domain of the Bayley-III at Week 24
- Change from baseline in the proportion of patients being able to feed without a gastrostomy or G-tube at Week 24
- Change from baseline in the Communicative Development Inventories scores at Week 24
- Change from baseline in the Parental Global Impression of Secretion Severity (PGIS-S) score at Week 24
- Change in the Parental Global Impression of Secretion Improvement (PGIS-I) score at Week 24

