2 STUDY OBJECTIVES, ENDPOINTS, AND ESTIMANDS

The objectives of the study are as follows:

- To determine the therapeutic dose of AT132
- To confirm the safety and efficacy of the therapeutic dose of AT132

The endpoints of the study are as follows:

Primary Efficacy Endpoint:

- Change from baseline in hours of ventilation support at Week 24

Key Secondary Efficacy Endpoint:

- Percentage of subjects achieving functionally independent sitting for at least 30 seconds at Week 24

Other Secondary Efficacy Endpoints:

- Time to reduction in required ventilator support to \leq 16 hours a day (only in subjects who require invasive ventilation) at Week 24
- Change from baseline in CHOP INTEND at Week 24
- Change from baseline in maximal inspiratory pressure (MIP) at Week 24
- Change from baseline in quantitative analysis of myotubularin expression in the muscle biopsy at Week 24
- Change from baseline in quality of life assessments at Week 24 (ie, the Assessment of Caregiver Experience with Neuromuscular Disease (ACEND) and Pediatric Quality of Life Inventory (PedsQL))
- Number (%) of age-appropriate clinically relevant gross motor function milestones attained through Week 24
- Percentage of subjects achieving full ventilator independence at Week 24
- Survival

Safety Endpoints:

- AEs, SAEs, and findings from safety laboratory tests, 12-lead electrocardiogram (ECG), echocardiograms (ECHOs), vital signs, growth parameters, physical examinations, liver ultrasounds, antibody formation (anti-AAV8, anti-MTM1), viral shedding, annualized hospitalization rate, annualized respiratory and non-respiratory SAE rate, and length of stay per hospitalization

Exploratory Endpoints:

- Time to unassisted sitting for 30 seconds or more at Week 24
- Change from baseline in the Motor Function Measure-32 (MFM-32) at Week 24
- Change from baseline in total raw score in the gross motor domain of the Bayley Scales of Infant and Toddler Development III (Bayley-III) at Week 24

- Change from baseline in total raw score in the fine motor domain of the Bayley-III at Week 24
- Change from baseline in the proportion of patients being able to feed without a gastrostomy or G-tube at Week 24
- Change from baseline in the Communicative Development Inventories scores at Week 24
- Change from baseline in the Parental Global Impression of Secretion Severity (PGIS-S) score at Week 24
- Change in the Parental Global Impression of Secretion Improvement (PGIS-I) score at Week 24

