1.1.3 Estimand

The estimand of the primary objective is defined by the following 5 attributes:

- Treatment: Single dose of AT132
- Population: Male participants with ventilator-dependent XLMTM, as defined by the inclusion/exclusion criteria of the study
- Endpoint: Change from baseline in hours per day of ventilation support at Week 24
- Intercurrent events and their corresponding strategies: For study discontinuation due to death or due to lack of efficacy, a composite strategy will be adopted, where participants with the intercurrent event before Week 24 having missing observation(s) after the intercurrent event will have those missing observations(s) imputed by unfavorable values ([Appendix 2](#))
- Population level summary: Mean change from baseline, by AT132 dose level

The estimand framework described above will be applied to all relevant primary and secondary efficacy endpoints.

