5.2 Appendix 2 Unfavorable Values for Efficacy Estimand Imputation

Endpoint	Variable	Imputed value after ICE occurrence through Week 48
Primary	Hours of ventilation support	24 hours
Key Secondary	Achieving functionally independent sitting for at least 30 seconds	No (0)
Secondary	CHOP INTEND Total Score	0
	MIP	0
	Myotubularin expression	0
	ACEND total score	0
	PedsQL Scale	0
	PedsQL Summary Score	0
	Number of age-appropriate gross motor function milestones achieved	0
	Full ventilator independence achieved	No

ICE = intercurrent event

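### On the ordinary reading of the SAP, a child who sits for 30 seconds and then dies before Week 24 would still be a success on the key secondary endpoint, because the composite rule fills only later missing visits

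*SAP*

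**What the plan says.** SAP 4.4.1.1 defines the key secondary endpoint as "Percentage of participants achieving functionally independent sitting for at least 30 seconds by Week 24". Sitting is scored visit by visit, from the motor milestone form or, failing that, Bayley-III item 26. SAP 4.4.1.2 words the main summary as follows: "participants achieving functionally independent sitting for at least 30 seconds by Week 24 will be summarized descriptively by low dose and high dose groups". A further table is planned there, in which sitting status "will be summarized descriptively by visit and dose level group".

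SAP 1.1.3 sets a composite strategy for study discontinuation due to death or lack of efficacy. Participants with such an event before Week 24 and missing observations afterwards "will have those missing observations(s) imputed by unfavorable values". It adds: "The estimand framework described above will be applied to all relevant primary and secondary efficacy endpoints". Appendix 2 (SAP 5.2) lists "Achieving functionally independent sitting for at least 30 seconds" as the key secondary variable, with imputed value No (0) after the event through Week 48.

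The protocol words the endpoint in two ways. The synopsis has "Percentage of subjects achieving functionally independent sitting for at least 30 seconds by Week 24", and Section 7.4.2.2.1 also uses *by*. Section 2 has "Percentage of subjects achieving functionally independent sitting for at least 30 seconds at Week 24". Protocol Section 7 makes the final SAP the analysis of record where the two documents differ.

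**The concern.** Listing sitting in Appendix 2 shows that the sponsor meant these intercurrent events to count against the child on this endpoint. The device chosen is imputation of later missing visits. That works for a status measured at a fixed visit. It does not work for an outcome that is met once and for all at any visit up to Week 24: a later imputed No cannot cancel an earlier observed Yes.

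The reported percentage is the whole result for this endpoint, since nothing is tested. If a child gained sitting and then died before Week 24, the report could show a responder on the key secondary endpoint beside the worst possible value on the primary. Protocol 1.5 reports four fatal outcomes with hepatobiliary failure among the causes, so death is a real intercurrent event in this trial.

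**Working it through.** The plan states no figure for this endpoint. Its only design calculation, N = 10, concerns ventilation hours and does not bear on the point. The check is therefore to apply the written rules to one child, and then to size the effect.

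**Can the pattern occur?** Yes. The schedules in Protocol 5.4 and 5.5 place motor milestone assessments at Weeks 4, 12, 16 and 24, so a Yes can be recorded before Week 24.

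**Hypothetical child:** No at Week 4, Yes at Weeks 12 and 16, death before Week 24. Appendix 2 fills Week 24 with No. The two Yes values are observed, so the rule leaves them alone.

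| Summary | Rule applied | Result |
|---|---|---|
| Primary endpoint, Week 24 (SAP 4.3.2) | missing value imputed | 24 hours |
| Key secondary, *by* read as at any visit up to Week 24 | one Yes is enough | Yes |
| Key secondary, *at Week 24* (Protocol Section 2) | imputed Week 24 value | No |
| By-visit table, Week 24 row (SAP 4.4.1.2) | imputed Week 24 value | No |

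**Which reading is the ordinary one?** The SAP 1.1.2 endpoint list uses *by Week 24* for sitting and *at Week 24* for full ventilator independence. SAP 4.4.1.2 also plans the by-visit table in addition to the main summary. If *by* meant status at Week 24, the main summary would largely repeat one row of that table.

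**Group sizes**
- Low dose: 6 children at the 8 July 2020 cutoff (Protocol 1.4.2). Three controls were still waiting for treatment (Protocol 3.1) and two were never dosed (SAP 1.3). So 6 + (3 − 2) = 7, assuming no replacement child was dosed.
- High dose: 17 at the same cutoff (Protocol 1.4.2). Children not yet dosed were then assigned to the lower dose.

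**Weight of one child**
- Low dose: 1/7 = 14.3 points (1/6 = 16.7 points if the group is 6).
- High dose: 1/17 = 5.9 points.

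**Number affected:** Protocol 1.5 places one of the four fatal outcomes at the lower dose and three at the higher. Neither death dates nor sitting status are given, so the count among them is 0 to 1 at low dose and 0 to 3 at high dose. If all three high-dose cases fitted, the shift would be 3/17 = 17.6 points. If none did, it would be zero.

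**The case against.** The strongest reply is that the SAP does not actually say this child is a success. It scores sitting by visit and has no rule for combining visits. Its *at* and *by* wording is loose elsewhere: time to ventilator support of 16 hours or less is *at Week 24* in the SAP and *by Week 24* in the protocol's analysis section. Appendix 2 does assign No to sitting after the event. This stands as a limit on certainty: the success classification is the ordinary reading, not a stated rule. It does not rescue the plan, because the alternative is that the classification is undefined.

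A second reply is that SAP 1.1.3 promises only to impute missing observations, so keeping an observed Yes breaks no written rule. That is correct as to the letter. But the section calls the strategy composite, and for this child the event does not enter the main key secondary result.

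A reader might infer that the imputation does nothing under *by Week 24*. That goes too far. SAP 4.1 bases percentages on participants with non-missing data, so the imputed No keeps a child who dies without any recorded sitting result in the denominator as a failure. It also fills the Week 24 row of the by-visit table.

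A reader might also extend the point to the other motor milestones. The documents do not support that. SAP 4.4.2.2.6 summarises them by visit among attending, age-eligible children, and takes each child's percentage at Week 24, where Appendix 2's zero can act.

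Finally, deaths are not hidden: survival by dose and deaths in the adverse event overview are both reported.

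**Conclusion.** The concern holds as a gap between the stated composite strategy and the key secondary definition. On the ordinary reading of the governing wording, an observed Yes followed by death or lack-of-efficacy discontinuation before Week 24 remains a success. Protocol Section 2 would classify the same child the other way, and the SAP has no explicit rule to settle it.

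One affected child is worth 14.3 points at low dose, which rests on the inferred group size of 7, or 5.9 points at high dose. Both figures assume that all dosed children enter the Full Analysis Set, which also requires a postdose efficacy assessment.

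A reader might conclude that response is overstated in this trial. The documents do not show that. No child is identified who sat and then died before Week 24, and the number may be zero. All summaries are descriptive (SAP Section 2), so no test or error rate is touched. The point is worth settling because the groups are small and the percentage is itself the reported result.

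**What to change.** In SAP 4.4.1.1, define success as sitting for at least 30 seconds at any post-dose assessment through Week 24, with no death and no discontinuation for lack of efficacy before Week 24. Keep the Appendix 2 entry, which still serves children without a recorded Yes and the by-visit table. Align the endpoint wording in Protocol Section 2 with this definition. No change is needed for the other milestones.

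If the sponsor prefers status at Week 24, or deliberately wants any achievement to count regardless of later death, the SAP should say so and reconcile SAP 1.1.3 and Appendix 2 with that choice.

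The cost is about one SAP sentence and one wording correction in the protocol. It uses data already collected. The downside is that the reported percentage may fall, by the amounts above for each child affected.
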